#### **6.3.2 Preparation and Administration**

Patients will take 160 mg (4 capsules) of enzalutamide orally once daily. Study drug should be taken as close to the same time each day as possible. Study drug can be taken with or without food.

### **6.4 Accountability and Compliance**

All study drugs will be stored at the investigational site in accordance with Good Clinical Practice (GCP) and Good Manufacturing Practices (GMP) requirements and the instructions given by the clinical supplies department of the Institution and will be inaccessible to unauthorized personnel.

The investigator, or a responsible party designated by the investigator, must maintain a careful record of the inventory and disposition of the agent (investigational or free of charge) using the NCI Drug Accountability Record or another comparable drug accountability form. (See the CTEP website at <http://ctep.cancer.gov/protocolDevelopment> for the “Policy and Guidelines for Accountability and Storage of Investigational Agents” or to obtain a copy of the drug accountability form).

### **6.5 Concomitant Medications**

All medication that is considered necessary for the subject’s welfare, and which is not expected to interfere with the evaluation of the study treatment, may be given at the discretion of the investigator. Collection of opioid-use in morphine equivalent will be captured on the case report forms

#### **Permitted**

- Treatment with non-conventional therapies (e.g., herbs [with the exception of St. John’s Wort], acupuncture) and vitamin / mineral supplements is acceptable provided that, in the opinion of the investigator, such treatment will not interfere with the trial endpoints.
- Subjects may receive standard of care for any underlying illness.

- In the event of neutropenia, anemia, or thrombocytopenia, subjects may receive appropriate supportive care (e.g., transfusion, biologic response modifiers such as G-CSF or GM-CSF, prophylactic antibiotics, antifungals and/or antivirals, hematopoietic growth factors). This supportive care should not substitute a recommended dose modification. Once the recommended dose modification has occurred, prophylactic G-CSF or GM-CSF may be used per institutional standard of care to prevent future events.
- Blood transfusions and erythropoietin are allowed during the study period but not within 4 weeks prior to the first dose of Radium.
- Bisphosphonates and denosumab are allowed at screening and throughout the study. Concomitant use with these agents should be documented in the patient records.
- LHRH agonists and antagonists are allowed at screening and throughout the study. Concomitant use with these agents should be documented in the patient records.
- If surgery is required during study drug treatment, the surgeon needs to be notified that the patient has been treated with a radioactive product and adequate precautions for radioactive protection should be applied during the surgical procedure. The patient should continue with study treatment if considered safe in the treating Investigator's opinion.

#### **Excluded concomitant therapies and medications**

- Concurrent anti-cancer therapy (chemotherapy, radiation therapy, surgery, immunotherapy, biologic therapy, or tumor embolization) other than Radium Ra 223 dichloride.
- Concurrent use of another investigational drug or device therapy (i.e., outside of study treatment) during, or within 4 weeks of trial entry (signing of the informed consent form).
- Clinical data indicate that enzalutamide is a strong inducer of CYP3A4 and a moderate inducer of CYP2C9 and CYP2C19. Concomitant use of enzalutamide with narrow therapeutic index drugs that are metabolized by CYP3A4 (e.g., alfentanil, cyclosporine, dihydroergotamine, ergotamine, fentanyl, pimozide, quinidine, sirolimus, tacrolimus), CYP2C9 (e.g., phenytoin, warfarin), and CYP2C19 (e.g., S-mephenytoin) should be avoided as enzalutamide may decrease their exposure. If co-administration with warfarin cannot be avoided, conduct additional INR monitoring.
- Co-administration of a strong CYP2C8 inhibitor (e.g., gemfibrozil) increased the composite  $AUC_{0-\infty}$  of enzalutamide plus its active metabolite in healthy volunteers; therefore, co-administration of enzalutamide with strong CYP2C8 inhibitors should be avoided if possible. If co-administration of enzalutamide with strong CYP2C8 inhibitors cannot be avoided, reduce the enzalutamide dose to 80 mg once daily. If co-administration of the strong inhibitor is discontinued, the enzalutamide dose

should be returned to the dose used prior to initiation of the strong CYP2C8 inhibitor.

The effects of CYP2C8 inducers on the PK of enzalutamide have not been evaluated in vivo. Co-administration of enzalutamide with strong or moderate CYP2C8 inducers (e.g., rifampin) may alter the plasma exposure of enzalutamide and should be avoided if possible. Selection of a concomitant medication with no or minimal CYP2C8 induction potential is recommended.

- The effects of CYP3A4 inducers on the PK of enzalutamide have not been evaluated in vivo. Co-administration of enzalutamide with strong CYP3A4 inducers (e.g., carbamazepine, phenobarbital, phenytoin, rifabutin, rifampin, rifapentine) may decrease the plasma exposure of enzalutamide and should be avoided if possible. Selection of a concomitant medication with no or minimal CYP3A4 induction potential is recommended. Moderate CYP3A4 inducers (e.g., bosentan, efavirenz, etravirine, modafinil, naftilin) and St. John's Wort may also reduce the plasma exposure of enzalutamide and should be avoided if possible.

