Hematologic evaluation of patients must be performed at baseline and prior to every dose of Radium Ra 223 dichloride. Before the first administration of Radium Ra 223 dichloride, the absolute neutrophil count (ANC) should be  $\geq 1.5 \times 10^9/L$ , the platelet count  $\geq 100 \times 10^9/L$ , and hemoglobin  $\geq 10 \text{ g/dL}$ . Before subsequent administrations of Radium Ra 223 dichloride, the ANC should be  $\geq 1 \times 10^9/L$  and the platelet count  $\geq 50 \times 10^9/L$ . If there is no recovery to these values within 6 to 8 weeks after the last administration of Radium Ra 223 dichloride, despite receiving supportive care, further treatment with Radium Ra 223 dichloride should be discontinued. Patients with evidence of compromised bone marrow reserve should be monitored closely and provided with supportive care measures when clinically indicated. Discontinue Radium Ra 223 dichloride in patients who experience life-threatening complications despite supportive care for bone marrow failure.

The safety and efficacy of concomitant chemotherapy with Radium Ra 223 dichloride have not been established. Outside of a clinical trial, concomitant use with chemotherapy is not recommended due to the potential for additive myelosuppression. If chemotherapy, other systemic radioisotopes, or hemibody external radiotherapy are administered during the treatment period, Radium Ra 223 dichloride should be discontinued.

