## 6.6 Protocol specified Duration of Therapy

Patients will receive up to 6 cycles of single agent enzalutamide or Radium Ra 223 dichloride and enzalutamide. If patients have a radium cycle delayed, the study visits will continue per the calendar and the dose will be missed. Treatment may be discontinued earlier if one of the following below criteria is met.

Subjects **must be withdrawn from the trial** (during protocol treatment and follow-up) for the following reasons:

- Subject withdraws consent from study treatment and study procedures. A subject must be removed from the trial at his / her own request or at the request of his / her legally acceptable representative. At any time during the trial and without giving reasons, a subject may decline to participate further. The subject will not suffer any disadvantage as a result.
- Subject is lost to follow-up.
- Anti-cancer therapy not prescribed by the study protocol is required.
- A treatment delay of more than 9 weeks between 2 injections of Radium Ra 223 dichloride.
- Disease Progression. During the protocol specified treatment, disease progression will be defined per PCWG2 progression criteria. After protocol defined therapy, the progression will be defined per clinical discretion of the treating clinician.
- Death.

Subjects **may be withdrawn from the study** for the following reasons:

- The subject is non-compliant with study drug, trial procedures, or both.

- If, in the investigator's opinion, continuation of the trial would be harmful to the subject's well-being.
- Development of a second cancer (other than superficial skin cancers, such as squamous cell carcinoma or basal cell carcinoma).
- Development of an intercurrent illness or situation which would, in the judgment of the investigator, significantly affect assessments of clinical status and trial endpoints.
- Deterioration of ECOG performance status to 4.
- Use of illicit drugs or other substances that may, in the opinion of the investigator, have a reasonable chance of contributing to toxicity or otherwise skewing trial result.

In all cases, the reason for withdrawal must be recorded in the CRF and in the subject's medical records.

A subject who discontinues study participation prematurely for any reason is defined as a "dropout" if the subject has already been enrolled / registered.

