### **7.1.3 Spinal Cord Compression**

If the patient experiences spinal cord compression during the treatment period, the patient should be treated for the event, and may receive further study drug administration if adequately recovered.

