### Analysis sets

The *safety population*, which includes all subjects who receive at least one dose of study drug, will be used for the safety analysis.

The *randomized population*, which includes randomized subjects with follow up to EOT or disease progression (which ever comes earlier) will be used for the primary efficacy analysis. This population *excludes* patients enrolled prior to randomization.

The *combined population* includes all subjects treated with enzalutamide + radium-223 or enzalutamide alone with follow up to EOT or disease progression (which ever comes earlier). This population includes subjects enrolled prior to randomization with sufficient follow up. The combined population will be used for secondary and exploratory analyses.

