#### **10.1.1 Primary Bone Marker Analysis**

Concomitant treatment with radium-223 (a bone targeting agent) and enzalutamide (a tumoricidal agent) is expected to decrease the level of N-telopeptides. As mentioned in the Background Section, serum N-telopeptides levels are inversely associated with overall survival, based on data from the SWOG 0421 trial. The primary endpoint for statistical analysis for this study will be the change in log 2 N-telopeptides from baseline to EOT or at disease progression (whichever comes earlier) between the randomization groups. If a bone marker test is missed at a given time point, every effort will be made to obtain the bone marker levels as early as possible. If two subsequent bone marker tests are missed, the patient will be excluded from the analysis. Equality of the change in log2 N-telopeptides between the treatment arms will be tested using an ANCOVA model with treatment group as the primary predictor and initial log 2 N-telopeptides as adjustment variable.

As a sensitivity analysis an F-test for equality of variance of final log2 N telopeptides will be performed. If the null hypothesis is rejected at the 0.1 significance level an additional ANCOVA model allowing for unequal variances will be fit.

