### Secondary and Exploratory Variables

The exploratory variables include:

- rPFS
- Time to radiological bone progression
- Total ALP response rate
- Time to total ALP progression
- Percentage change in total ALP
- PSA response rate
- Time to PSA progression
- Time to first skeletal related event (as defined below)
- OS for 2 years after enrollment
- Percent change in opioid requirement (in morphine equivalent) during protocol treatment.

Skeletal related events include the following:

- Time to occurrence of first use of external beam radiotherapy to relieve skeletal symptoms
- Time to occurrence of first tumor related orthopedic surgical intervention
- Time to occurrence of first spinal cord compression
- Time to occurrence of first new symptomatic pathological bone fractures (vertebral and non-vertebral)

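### The rules on palliative bone radiotherapy and surgery conflict, and read literally they can drop patients from the primary N-telopeptide comparison after a bone event

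*Combined protocol and SAP*

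**What the plan says.** All quotations are from the combined protocol and SAP.

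**Text that points to withdrawal**
- Section 6.5, excluded therapies: "Concurrent anti-cancer therapy (chemotherapy, radiation therapy, surgery, immunotherapy, biologic therapy, or tumor embolization) other than Radium Ra 223 dichloride". Palliative treatment of bone is not exempted.
- Section 6.6, under mandatory withdrawal on treatment and in follow-up: "Anti-cancer therapy not prescribed by the study protocol is required".

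**Text that points to continuing**
- Section 6.5 (permitted therapies) and Section 7.1.4 let a patient who needs surgery stay on study treatment if the investigator thinks it safe.
- Section 7.1.3, on cord compression: "the patient should be treated for the event, and may receive further study drug administration if adequately recovered".
- Section 7.1.6 allows study treatment to go on after a pathological fracture.
- Sections 9.2 and 9.4.1 follow patients for two years. For survival, Section 9.4.1 says this holds whatever the date of progression.

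**Endpoint**
- Section 10.2 lists as its first skeletal-event component "Time to occurrence of first use of external beam radiotherapy to relieve skeletal symptoms", and as its second, tumor-related orthopedic surgery.

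**Who is in the primary analysis**
- Section 10, Analysis sets: "randomized subjects with follow up to EOT or disease progression (which ever comes earlier) will be used for the primary efficacy analysis".
- Section 10.1.1: "If two subsequent bone marker tests are missed, the patient will be excluded from the analysis".
- Section 6.6 lets the investigator replace patients who are withdrawn before the C3D1 draw or are not evaluable for the primary objectives.
- Section 8 dates the EOT visit two ways: four weeks after the last treatment (note 6) and four weeks after C6D1 (note 10). Note 7 adds a marker sample at progression.

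**The concern.** Every patient enters with symptomatic bone metastases (5.1.8), so radiotherapy to a painful lesion is a foreseeable event. Section 6.5 names radiation therapy and surgery as examples of anti-cancer therapy, so an investigator who follows 6.5 and 6.6 to the letter withdraws the patient. One who follows Section 7.1 may keep him on. The protocol does not say which governs.

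The statistical consequence comes from the analysis set, which is not all randomized patients. Needing bone radiotherapy happens after randomization and is plausibly related to bone turnover, the quantity being compared. If it ends serum collection, patients with a worse bone course are selectively missing from the N-telopeptide contrast. Literal withdrawal from follow-up would also cut into the two-year survival data. Because the trial is open label and replacement is discretionary, the treatment assignment is known when these decisions are made.

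**Working it through.** **1. Route out of the primary analysis**

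Suppose a patient is irradiated and withdrawn under 6.6.
- *PCWG2 progression also present:* a progression sample is due, so he has a final value and stays in.
- *No progression, EOT dated from last treatment (note 6):* a closing sample may exist and he may stay in.
- *No progression, EOT dated from C6D1 (note 10):* no closing sample is called for. If irradiated before C5D1, he misses at least two subsequent draws and is excluded under 10.1.1. If irradiated after C5D1, he misses only EOT, so that rule is not met, but the analysis-set definition may still exclude him.

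Only patients with neither progression nor a closing sample are at risk.

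**2. How many could be affected**

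The plan gives no radiotherapy rate. Section 3.1.4 gives median time to first skeletal event in the cited phase III trial as 15.6 months (radium) and 9.8 months (placebo). Assume exponential times, so F(t) = 1 − 0.5^(t/median), with 30.44 days per month.

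- Day 168 = 5.52 months. Radium: 1 − 0.5^(5.52/15.6) = 0.217; 27 × 0.217 = 5.9.
- Placebo: 1 − 0.5^(5.52/9.8) = 0.323; 12 × 0.323 = 3.9.
- The Section 2.2 medians (13.6 and 8.4 months) give 0.245 and 0.366, or 6.6 and 4.4 patients.

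Split by draw, using F(56) = 0.079 and 0.122, and F(112) = 0.151 and 0.229:

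| First skeletal event | Combination, of 27 | Control, of 12 |
|---|---|---|
| Before C3D1 (day 56) | 2.1 | 1.5 |
| C3D1 to C5D1 (days 56–112) | 2.0 | 1.3 |
| C5D1 to EOT (days 112–168) | 1.8 | 1.1 |
| Total | 5.9 | 3.9 |

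All rows count every skeletal event, not radiotherapy alone, and do not subtract patients who progress first. If half were radiotherapy (an assumption), the middle row falls to about 1.0 and 0.6. The allowance for inevaluable patients is 50 − 47 = 3.

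**3. Effect on power**

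Inputs from Section 10: difference 1.14, SD 1.14, correlation 0.50, two-sided 0.05, 27 versus 12. SD of change = 1.14 × √(2 × (1 − 0.50)) = 1.14. The plan states 85% power for a two-sample t-test. The noncentral t gives 80.2% and the normal approximation 82.2%, so 85% does not reproduce. That is a separate matter, and 80.2% is the reference here. The ANCOVA residual SD is 1.14 × √(1 − 0.25) = 0.987.

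| Share of events causing loss | Remaining | t-test | ANCOVA |
|---|---|---|---|
| None | 27 vs 12 | 80% | 90% |
| 25% | 26 vs 11 | 77% | 88% |
| 50% | 24 vs 10 | 73% | 84% |
| 100% | 21 vs 8 | 64% | 76% |

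**4. Effect on bias**

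Assume correlation ρ between marker change and radiotherapy risk. Removing the worst proportion p shifts an arm's mean down by 1.14 × ρ × φ(c)/(1 − p), where c = Φ⁻¹(1 − p). For p = 0.32 the ratio φ(c)/(1 − p) is 0.526; for p = 0.22 it is 0.380. The arm difference shrinks by 1.14 × ρ × (0.526 − 0.380), which is 0.05 at ρ = 0.3 and 0.08 at ρ = 0.5, against a design difference of 1.14. Loss of 33% versus 0% would give 0.19 to 0.31, but nothing in the documents supports that pattern.

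**The case against.** The strongest reply is that nothing in the plan says a patient given bone radiotherapy leaves the primary analysis. Progressors have a sample, and under note 6 an early stopper may have one too. Because Sections 6.5 and 7.1.4 permit surgery although surgery is on the excluded list, that list may be aimed at treatment with anti-cancer intent, so palliative treatment would not trigger 6.6. Section 6.6 is also loosely worded: it lists progression as a reason for withdrawal in follow-up, while 9.4.1 keeps progressors in survival follow-up.

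Most of this stands. It makes the loss conditional. It does not remove the conflict, because the text names radiation therapy without qualification and the closing sample is dated two ways.

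Several stronger readings are tempting but unsupported:
- *The endpoint contradicts the withdrawal rule.* An event can be counted and also end treatment. A time-to-first analysis still captures the first radiotherapy.
- *The drug-information text authorizes focal radiotherapy.* It says "If chemotherapy, other systemic radioisotopes, or hemibody external radiotherapy are administered during the treatment period, Radium Ra 223 dichloride should be discontinued", which states when radium stops and nothing more. The background care in the cited phase III trial sets no rule here. Section 7.1.3 does not name radiotherapy.
- *Sites will handle this differently.* The trial is single-center. Inconsistency could arise only between investigators or patients.
- *The 6.5 bullet names only radium because it was not updated for two arms.* The initial single arm already combined radium with enzalutamide, so the change of design does not explain the omission.

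**Conclusion.** The conflict between Sections 6.5, 6.6, 7.1 and 9 is clear from the text. The route by which it can remove patients from the primary analysis is real but conditional on there being neither PCWG2 progression nor a closing sample.

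The upper bound is about 6 of 27 and 4 of 12 patients by day 168. It assumes exponential times, radium-versus-placebo medians, every skeletal event being radiotherapy, and every such patient lost. The true number is likely much smaller: about 2 and 1.3 have a first skeletal event of any kind between C3D1 and C5D1, and enzalutamide in both arms would be expected to lower the rates.

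A reader might infer that the primary contrast is materially biased against the combination. The documents do not establish this. The imbalance is extrapolated from a placebo comparison, and under moderate assumptions the shift is 0.05 to 0.08 log2 units, toward no difference. Loss of evaluable patients is the larger concern: even if a quarter of the events led to loss, (5.9 + 3.9) × 0.25 ≈ 2.5 patients would go, close to the whole allowance of 3.

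**What to change.** 1. The sponsor should reconcile Sections 6.5, 6.6, 7.1.3, 7.1.4, 7.1.6 and 10.2 on whether palliative bone radiotherapy and tumor-related orthopedic surgery count as excluded anti-cancer therapy. Whether study drug continues is the sponsor's decision.
2. Under either rule, separate stopping study drug from leaving the study in Section 6.6. Record the event as a skeletal event, and continue the scheduled marker draws and two-year follow-up where the patient consents.
3. Define the EOT sample for early stoppers, reconciling notes 6 and 10 of Section 8.
4. Amend the analysis-set definition and the missed-test rule in Section 10 so that these patients stay in the primary analysis.
5. Add one sensitivity analysis that sets aside post-radiotherapy values. It should not carry baseline forward for patients irradiated before C3D1, since that forces a change of zero. Multiple imputation from baseline and arm, with a range of shifts, would serve.
6. Align the 6.5 exemption with 5.2.5, which exempts protocol treatment generally instead of radium alone.

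The cost is amendment wording and one extra analysis. The draws are already scheduled and no new assay is needed.

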## 6.6 Protocol specified Duration of Therapy

Patients will receive up to 6 cycles of single agent enzalutamide or Radium Ra 223 dichloride and enzalutamide. If patients have a radium cycle delayed, the study visits will continue per the calendar and the dose will be missed. Treatment may be discontinued earlier if one of the following below criteria is met.

Subjects **must be withdrawn from the trial** (during protocol treatment and follow-up) for the following reasons:

- Subject withdraws consent from study treatment and study procedures. A subject must be removed from the trial at his / her own request or at the request of his / her legally acceptable representative. At any time during the trial and without giving reasons, a subject may decline to participate further. The subject will not suffer any disadvantage as a result.
- Subject is lost to follow-up.
- Anti-cancer therapy not prescribed by the study protocol is required.
- A treatment delay of more than 9 weeks between 2 injections of Radium Ra 223 dichloride.
- Disease Progression. During the protocol specified treatment, disease progression will be defined per PCWG2 progression criteria. After protocol defined therapy, the progression will be defined per clinical discretion of the treating clinician.
- Death.

Subjects **may be withdrawn from the study** for the following reasons:

- The subject is non-compliant with study drug, trial procedures, or both.

- If, in the investigator's opinion, continuation of the trial would be harmful to the subject's well-being.
- Development of a second cancer (other than superficial skin cancers, such as squamous cell carcinoma or basal cell carcinoma).
- Development of an intercurrent illness or situation which would, in the judgment of the investigator, significantly affect assessments of clinical status and trial endpoints.
- Deterioration of ECOG performance status to 4.
- Use of illicit drugs or other substances that may, in the opinion of the investigator, have a reasonable chance of contributing to toxicity or otherwise skewing trial result.

In all cases, the reason for withdrawal must be recorded in the CRF and in the subject's medical records.

A subject who discontinues study participation prematurely for any reason is defined as a "dropout" if the subject has already been enrolled / registered.

A subject who, for any reason (e.g. failure to satisfy the selection criteria), terminates the study before the time point used for the definition of "dropout" (see above) is regarded a "screening failure".

Patients withdrawn prior to the C3D1 blood draw or determined to be not evaluable for the primary objectives may be replaced per investigators discretion.

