### **7.1 Dose Modifications Radium Ra 223 Dichloride**

Every effort should be made to administer the full dosing regimen of Radium Ra 223 dichloride. Adjustment of dose level is not permitted.

Study visits during the treatment period should occur at 4 weeks intervals (within a window of  $\pm$  7 days). If a patient requires a toxicity related dose delay of more than 9 weeks between 2 injections, then the patient must be discontinued from the study. If patients have a radium cycle delayed, the study visits will continue per the calendar and the dose will be missed. Dosing delays may be instituted under the following circumstances:

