## 8 STUDY CALENDAR

1 cycle = 28 days

- 1 ALL Pre-study / Screening procedures should be completed within 4 weeks of study enrollment - with the exception of laboratory tests which need to be completed within 2 weeks prior to study enrollment.
- 2 Hematology includes CBC with differential and platelets. CBC must be completed within 2 weeks of study enrollment and prior to treatment ( $\pm$  7 days) on day 1 of each cycle.
- 3 Chemistry includes Albumin, Alkaline Phosphatase, Aspartate Aminotransferase, Alanine Aminotransferase, Total Bilirubin, Calcium, Carbon Dioxide, Creatinine, Chloride, Glucose, Potassium, Protein, Sodium, and Urea Nitrogen.
- 4 Bone alkaline phosphatase (BAP) should be done every four weeks until the end of treatment visit or disease progression (whichever comes earlier).
- 5 PSA is required within 28 days at screening, on day 1 of each cycle and at the end of treatment visit. PSA laboratory assessments should be performed every 4 – 6 weeks after the end of treatment visit until disease progression, or the start of another treatment.
- 6 CT and bone scans should be conducted at screening, end of cycle 3 (prior to C4D1 treatment), and at the end of treatment visit (4 weeks post last treatment). Follow-up scans will be performed as clinically indicated until documented PD per treating clinician or until the start of another treatment. Scans should include CT scan of abdomen and pelvis. Imaging of the chest is only required if clinically indicated.
- 7 Bone markers collected at baseline (C1D1), C3D1, C5D1, EOT and at disease progression (whichever comes earlier); to include procollagen Type 1 intact N-terminal Propeptide (NTP) and resorption (N-telopeptide [NT], C-Telopeptide beta-cross linked [CTB] and pyridinoline).
- 8 Radium Ra 223 dichloride 55 kBq/kg\*\* on day 1 of every cycle for up to 6 cycles (\*\* 50 kBq/kg prior to implementation of the NIST update).
- 9 Enzalutamide 160 mg daily.
- 10 End of Treatment visit should be conducted 4 weeks post C6D1.
- 11 For all patients who receive study treatment, follow-up for survival will occur approximately every 8 weeks following end of treatment or as clinically indicated for up to 2 years post enrollment or death.
- 12 All procedures for day 1 of each treatment cycle have a  $\pm$  7 day window.
- 13 Subjects receiving concomitant medication with warfarin should have INR monitored more frequently as clinically indicated.

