### **9.4 Efficacy**

#### **9.4.1 Pre-study Documentation of Progressive Disease**

Patients must have documented PD either by radiographic or PSA criteria as defined in Inclusion Criterion # 5.1.6 in Section 5.1.

Both radiographic PD and PSA PD must be assessed to evaluate eligibility; however, only one criterion (radiographic PD or PSA PD) must be met for Inclusion Criterion # 5.

PSA will be assessed at time points shown in the Schedules of Events.

Scans (CT/MRI) of the abdomen and pelvis and radionuclide bone scans will be used to monitor and assess disease response and progression, as described in the Schedule of Events. CT imaging of the chest is only required at baseline if clinically indicated. If disease is found in the chest, lesions should be followed by CT scan. The imaging modality for each patient must remain constant throughout the study. Additional scans should be performed at the

investigator's discretion if progression is suspected or to confirm the existence of bone lesions.

During the protocol specified treatment, disease progression will be defined per PCWG2 progression criteria. After completion of protocol defined therapy, the progression will be defined per clinical discretion of the treating clinician. Patients who complete study treatment without documented disease progression will continue to be followed by scans and PSA per the follow-up outlined in the study calendar until progression is seen or new treatment is started. All patients, regardless of date of progression, will be followed for 2 years post study enrollment for overall survival.

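### Section 6.6 withdraws patients from follow-up at progression, new therapy or a long radium gap, which contradicts the planned 2-year survival follow-up of all treated patients

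*Combined protocol and SAP*

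**What the plan says.** Section 6.6 opens as a rule on stopping treatment: "Treatment may be discontinued earlier if one of the following below criteria is met". The list that follows is framed more widely. Subjects must be withdrawn from the trial itself, "during protocol treatment and follow-up) for the following reasons". Besides consent withdrawal, loss to follow-up and death, the mandatory reasons are:

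- disease progression, including after treatment has ended: "After protocol defined therapy, the progression will be defined per clinical discretion of the treating clinician";
- new therapy: "Anti-cancer therapy not prescribed by the study protocol is required";
- a radium gap: "A treatment delay of more than 9 weeks between 2 injections of Radium Ra 223 dichloride".

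Section 7.1 repeats the last item for toxicity-related delays over 9 weeks: "then the patient must be discontinued from the study".

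Four other places point the other way. Section 9.4.1 states: "All patients, regardless of date of progression, will be followed for 2 years post study enrollment for overall survival". Study calendar note 11 applies to every patient who receives study treatment: "follow-up for survival will occur approximately every 8 weeks following end of treatment", up to 2 years after enrollment or death. Sections 4.4 and 9.2 also give two years of follow-up. Calendar notes 5 and 6 end only PSA and scan follow-up at progression or new treatment.

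Overall survival at 2 years is a secondary objective (1.2.5). Section 10.2 makes its analysis descriptive, by Kaplan-Meier.

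**The concern.** A patient who progresses at month 5 must leave follow-up under 6.6 and must stay in it under 9.4.1. Staff who read 6.6 would close the record, and staff who read 9.4.1 would keep contacting the patient. Practice could differ from one patient to the next.

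If 6.6 is followed, survival is censored at progression or next therapy. Kaplan-Meier estimation assumes that censored patients have the same later risk as those still followed. Patients who have just progressed would be expected to have a higher risk of death, so the curve would tend to overstate survival.

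The radium-gap item adds an imbalance, because only the combination arm receives radium. Grade 3 or 4 cytopenia is one of the stated grounds for delay (7.1.1), so loss by this route is linked to toxicity and occurs in one arm. There is also a possible effect before progression. The randomized population in section 10 requires follow-up to EOT or progression, and the EOT visit is set 4 weeks after C6D1 (note 10). A patient withdrawn for a radium gap before EOT, without progression, might have neither and so drop out of the primary N-telopeptide analysis.

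**Working it through.** **1. Does 6.6 really reach follow-up?** Three features say so. The list names follow-up in its own words. Its progression item covers progression after protocol therapy, when no protocol treatment is left to stop. And 6.6 contains no exception for survival contact. For progression, 9.4.1 contradicts it directly. For new therapy and the radium gap, the contradiction comes through the general wording of note 11 and sections 4.4 and 9.2, because 9.4.1 names only progression.

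**2. Deaths expected within 2 years.** The protocol gives no expected number of deaths, so there is no figure to reproduce. As an illustration, assume exponential survival: P(death by 24 months) = 1 − 2^(−24/median), applied to 47 patients (4.2).

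| Median OS, months | Source | P(death) | Deaths of 47 |
|---|---|---|---|
| 14.9 | radium-223 arm, 3.1.4 | 0.673 | 31.6 |
| 18.4 | enzalutamide arm, 2.1 | 0.595 | 28.0 |
| 22.4 | NTx at or below median, Table 1 | 0.524 | 24.6 |

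These are total deaths, not deaths lost.

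**3. Share unobserved if 6.6 is applied literally.** Only deaths that occur before any progression would be seen. The documents give no progression time for this trial, so the median p is an assumption. The value 8.3 months, the median enzalutamide treatment duration in 3.2.1, serves as one proxy.

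- *Model A: a fraction f of first events are deaths without progression.* Observed deaths = f × (1 − 2^(−24/p)), with f from 0.05 to 0.30 and p from 6 to 12 months. Highest loss: f = 0.05, p = 12, median OS 14.9 gives 0.05 × 0.75 = 0.0375 observed (1.8 of 47), so 1 − 0.0375/0.673 = 94% are lost. Lowest loss: f = 0.30, p = 6, median OS 22.4 gives 0.30 × 0.9375 = 0.281 observed (13.2 of 47), so 1 − 0.281/0.524 = 46% are lost.
- *Model B: independent exponential times to progression and death.* This favors capture of deaths. With a = ln2/p and b = ln2/median OS, observed deaths = b/(a+b) × (1 − e^(−24(a+b))). At p = 18 and median OS 14.9, 0.476 of patients have an observed death, so 1 − 0.476/0.673 = 29% are lost. At p = 6 and median OS 22.4, 0.205 is observed, so 61% are lost. At p = 8.3 the loss is 49% to 52% across the three medians.

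The overall range is 29% to 94%.

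**4. When does the radium gap arise?** Sections 6.6 and 7.1 both say that a delayed dose is missed and visits continue by calendar. One missed dose leaves 2 × 4 = 8 weeks between injections, and two in a row leave 3 × 4 = 12. Two consecutive misses therefore exceed 9 weeks. With the ±7-day window at both ends, a single miss can reach 8 + 1 + 1 = 10 weeks. The documents give no frequency for either.

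**The case against.** The strongest defense is that 6.6 is headed and introduced as a rule about therapy, while 9.4.1 deals specifically with progressed patients and keeps them in survival follow-up, as does note 11 for everyone treated. On this view the practical reading is to stop treatment and keep contact. This is a fair account of what staff may well do, and it defeats any flat prediction of loss. It does not remove the contradiction, because 6.6 names follow-up and nothing ranks the sections.

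Four stronger readings are tempting and not supported:

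- *Most deaths will be lost.* This needs 6.6 to override 9.4.1 and also an assumed progression time. At the low end of the range, most deaths are still captured.
- *The 60% to 67% dying by 24 months (at medians of 18.4 and 14.9 months) is the share lost.* It is the total expected. The medians also come from other populations: the enzalutamide trial included 23% with lung or liver involvement (3.2.2), whereas this trial excludes visceral metastases.
- *The plan censors survival at progression.* No section says so, and 10.3 leaves further censoring details to the SAP.
- *Toxicity dropouts are lost from one arm only.* Section 6.6 also permits withdrawal in either arm for harm or intercurrent illness. Section 7.1.1 ends study drug for Grade 3 or 4 cytopenia lasting over 14 days, which may often come before a gap of over 9 weeks. Only the radium-gap route is arm-specific.

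It also stands that overall survival is secondary and descriptive, and that losing follow-up after progression does not touch the primary marker endpoint, which is measured at EOT or progression.

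**Conclusion.** The contradiction is certain from the text: 6.6, with the matching phrase in 7.1, against 4.4, 9.2, 9.4.1 and calendar note 11. Its consequence is conditional. If 6.6 were applied literally, a substantial share, possibly most, of about 25 to 32 expected deaths could go unobserved. Those counts rest on exponential survival with borrowed medians, and the share lost rests further on assumed progression timing.

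The harm falls mainly on the 2-year survival endpoint, with a component specific to the combination arm through the radium gap. An effect on the primary analysis is possible only for patients withdrawn by that route before EOT without progression, and its frequency is unknown. This is worth correcting because the repair is cheap and missed survival data cannot always be recovered.

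**What to change.** Reconcile 6.6 and 7.1 with 4.4, 9.2, 9.4.1 and note 11 by separating three decisions:

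- (a) end of protocol treatment;
- (b) end of PSA and scan follow-up, as calendar notes 5 and 6 already set it;
- (c) withdrawal from survival follow-up, only for consent withdrawal, loss to follow-up or death.

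State that patients who stop treatment for any other reason stay in the planned 8-weekly survival follow-up to 2 years and have the already scheduled EOT bone-marker sample where possible. Align the two statements of the radium-gap item, since 7.1 limits it to toxicity-related delays and 6.6 does not. The clinical stopping criteria themselves are not in question here and should be left as they are.

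The cost is a wording amendment, with no added survival contacts. One item is not free. Section 9.2 implies two years of follow-up for first skeletal events, but note 11 names survival only. Recording skeletal events at the 8-weekly contacts would need a small CRF addition.
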